4. STUDY DESIGN

4.1 Overall design

This is an open-label, two-part study to assess the safety, tolerability, pharmacokinetics and clinical efficacy of acalabrutinib in Chinese adult subjects with R/R MCL, R/R CLL and other B-cell malignancies. The study is divided into 2 parts: Phase 1 portion and Phase 2 portion.

Phase 1 portion

The primary objective of Phase 1 portion is to assess the safety, tolerability and pharmacokinetics of acalabrutinib in Chinese subjects with R/R B-cell Malignancies and the secondary objective is to access the efficacy of acalabrutinib in Chinese subjects with R/R B-cell malignancies. Approximately 12 subjects will be enrolled in the Phase 1 portion including subjects with R/R non-GCB diffuse large B-cell lymphoma (DLBCL), follicular lymphoma (FL), mantle cell lymphoma (MCL), chronic lymphocytic leukemia (CLL), Small Lymphocytic Lymphoma (SLL).

Subjects will be administered a single dose of acalabrutinib 100 mg at Cycle 0 Day 1. During the following 2 days wash-out period, intensive PK samples will be collected before and after the first dose until pre-dose at Cycle 1 Day 1. From Cycle 1 Day 1, subjects will be administered multiple doses of acalabrutinib 100 mg BID on a continuous schedule (28 days per cycle). Intensive PK samples will be collected on Cycle 1 Day 8 for 12-hour PK profile at steady state. Additional sparse PK samples will be collected on Cycle 1 Day 28 to assess time-dependent changes. Treatment with acalabrutinib may be continued for Cycle 2 onwards until

disease progression or any other treatment discontinuation criterion is met. All subjects who discontinue the study drug will have a safety follow-up visit 30 (+7) days after the last dose of study drug.

The dose regimen of multiple doses of 100 mg BID has been found to be safe/tolerable and potentially effective in overseas clinical studies in Western and Asian subjects. In case of intolerable toxicity, dose reduction to 100 mg QD may be considered (details in Section [6.6.2](#)). Subjects will continue on treatment with acalabrutinib until a treatment discontinuation criterion is met.

Phase 2 portion

Phase 2 portion is to further evaluate clinical efficacy, safety and tolerability in subjects with R/R MCL and R/R CLL. Evaluation of efficacy and safety will be performed independently for each cohort.

Cohort A

Cohort A is to evaluate clinical efficacy, safety and tolerability in subjects with pathologically documented MCL who have relapsed after, or were refractory to, ≥ 1 (but not >5) prior treatment regimens. Approximately 33 R/R MCL subjects will be enrolled to receive 100 mg of acalabrutinib BID in repeated 28-day cycles.

Cohort B

Cohort B is to evaluate clinical efficacy, safety and tolerability in subjects with CLL who have failed from ≥ 1 prior systemic therapies. Approximately 60 R/R CLL subjects will be enrolled to receive 100 mg of acalabrutinib BID in repeated 28-day cycles.

Treatment with acalabrutinib may be continued until disease progression or any other treatment discontinuation criterion is met. Dose modification provisions are outlined in Section [6.6.2](#). Note: Temporary withholding of study drug for as little as 7 days can cause a transient worsening of disease and/or of constitutional symptoms. Refer to Section [7.1](#) for more information on assessing disease progression under these circumstances. An early termination visit is required for any subjects who permanently discontinue study drug for any reason (except for death, lost to follow up or withdrawal of consent), including disease progression. In addition to the early termination visit, all subjects who discontinue study drug will have a safety follow-up visit 30 (+ 7) days after his or her last dose of study drug.

All subjects will have hematology, clinical chemistry, and urinalysis safety panels done at screening. Once dosing commences (Cycle 1 Day 1), all subjects will be evaluated for safety, including hematology and clinical chemistry at regular basis.

Tumor assessments for R/R MCL subjects will be performed at 8- to 12-week intervals throughout the study. Tumor assessments for R/R CLL subjects will be performed at 12- to 24-week intervals throughout the study. Refer to Section 1.1 for a comprehensive list of study assessments and their timing. The end of trial is defined as the 3rd analyses for R/R CLL subjects of Phase 2 cohort B, which will occur approximately 24 months after the last R/R CLL subject enrolled into Phase 2.

The primary efficacy analyses (R/R MCL and R/R CLL subjects) will be based on Blinded Independent Central Review (BICR) assessment.

4.1.1 Study Conduct Mitigation During Study Disruptions Due to Cases of Civil Crisis, Natural Disaster, or Public Health Crisis

The guidance given below supersedes instructions provided elsewhere in this CSP and should be implemented only during cases of civil crisis, natural disaster or public health crisis (eg, during quarantines and resulting site closures, regional travel restrictions and considerations if site personnel or study participants become infected with severe acute respiratory syndrome coronavirus 2 [SARS-CoV-2] or similar pandemic infection), which would prevent the conduct of study-related activities at study sites, thereby compromising the study site staff or the participant's ability to conduct the study. The investigator or designee should contact the study sponsor to discuss whether the mitigation plans below should be implemented.

To ensure continuity of the clinical study during a civil crisis, natural disaster, or public health crisis, changes may be implemented to ensure the safety of study participants, maintain compliance with GCP, and minimize risks to study integrity. Where allowable by local health authorities, ethics committees, health care provider guidelines (eg, hospital policies) or local government, these changes may include the following options:

- Obtaining consent/reconsent for the mitigation procedures (note, in the case of verbal consent/reconsent, the informed consent form (ICF) should be signed at the participant's next contact with the study site).
- Telemedicine visit: Remote contact with the participants using telecommunications technology including phone calls, virtual or video visits, and mobile health devices.

For further details on study conduct during civil crisis, natural disaster, or public health crisis, refer to [Appendix F](#)

4.2

CCI

tolerability and PK data of acalabrutinib in in Chinese population. The study population of
CC1

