- z. Acalabrutinib should be taken under fasting condition (at least 10 hours before dosing and at least 4 hours after dosing) in the Phase 1 portion morning dose of Cycle 0 Day 1 and Cycle 1 Day 8.
- aa. Adverse Events will be collected from time of signature of informed consent form until 30 days after the last dose of study treatment or the start of new anticancer therapy (whichever comes first). The safety follow-up period is defined as 30 (+7) days after study treatment is discontinued.
- bb. Survival status should be assessed at the time of the planned final analysis and additional milestone analyses as applicable.
- cc. Subjects will receive a drug diary to record the specific time each dose was taken and to record reasons for any missed doses. Subject compliance will be assessed at each study visit.
- dd. For R/R CLL subjects only.

Table 2 Schedule of Activities (Phase 2 Cohort A – R/R MCL)

	Screening ^a	Cycle 1					Cycle 2		Cycle 3	Cycle 4	Cycles 5-12	Cycles 15, 18, 21, ≥24 ^b	EoT ^c	Safety Follow Up ^c	Post-treatment disease Follow up ^d	Survival Follow up ^e	Details in Section
Day of Each Cycle	-28 to -1	1	8	15	22	28	15	28	28	28	28	28					
Visit Window (Days)		0	± 2					± 2	± 2	± 2	± 2	± 3	+ 7	+ 7	± 7	± 7	
Informed consent	x																Appendix A3
Inclusion/exclusion criteria	x																5.1 & 5.2
Routine clinical procedures																	
Demography	x																
Medical history	x																8
B symptoms	x																8.1.4
Physical examination ^f /Vital signs ^g	x	x	x	x	x	x	x	x	x	x	x	x	x	x			8.2.2 & 8.2.3
ECOG status	x	x	x	x	x	x	x	x	x	x	x	x	x	x			8.2.5
ECG ^h	x		x		x		x	x	x	x	x	x	x	x			8.2.4

Table 2 Schedule of Activities (Phase 2 Cohort A – R/R MCL)

	Screening ^a	Cycle 1					Cycle 2		Cycle 3	Cycle 4	Cycles 5-12	Cycles 15, 18, 21, ≥24 ^b	EoT ^c	Safety Follow Up ^c	Post-treatment disease Follow up ^d	Survival Follow up ^e	Details in Section
Day of Each Cycle	-28 to -1	1	8	15	22	28	15	28	28	28	28	28					
Visit Window (Days)		0	± 2					± 2	± 2	± 2	± 2	± 3	+ 7	+ 7	± 7	± 7	
Concomitant medications		←											→				6.5
Routine safety assessments																	
Pregnancy test ⁱ	X	x	As clinically indicated														8.1.3
Hematology ^j	X	x ^r	x	x	x	x	x	x	x	x	x	x	x	x	x		8.1.3
Clinical chemistry ^k	X	x ^r	x	x	x	x	x	x	x	x	x	x	x	x	x		8.1.3
Hepatitis and HIV serology ^o	X																8.1.3

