- 23 Ongoing immunosuppressive therapy, including systemic (e.g., IV or oral) corticosteroids of underlying disease within 2 weeks before the first dose of study drug. Note: Subjects may use topical or inhaled corticosteroids or steroids (\leq 20 mg prednisone equivalent/day for \leq 2 weeks) as a therapy for comorbid conditions. During study participation, subjects may also receive systemic (e.g., IV or oral) corticosteroids as needed for treatment-emergent comorbid conditions.
- 24 Use of a strong inhibitor or inducer of CYP3A within 7 days before dose of study drug or expected requirement for use of a CYP3A inhibitor or inducer (including herbal medication known to modulate CYP3A4 enzyme activity) during the first 28 days of administration of study drugs.
- 25 Received a live virus vaccination within 28 days of first dose of study drug.
- 26 History of allergy or hypersensitivity to any component of the acalabrutinib formulation

Prior/concurrent clinical study experience

- 27 Concurrent participation in another therapeutic clinical trial.

Other exclusions

- 28 Breastfeeding or pregnant (breastfeeding is not allowed during treatment and until 2 days after the end of treatment. However, resumption of breastfeeding 2 days after the last dose is allowed.)

29 Judgment by the investigator that the subject should not participate in the study if the subject is unlikely to comply with study procedures, restrictions and requirements.

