6.1 Treatments administered

6.1.1 Investigational products

Investigational product	Dosage form and strength	Manufacturer
Acalabrutinib	100 mg, opaque size 1 hard capsule with a yellow and blue	CCI [REDACTED]

Acalabrutinib is intended to be administered orally once or twice daily with approximately 240 mL of water. Acalabrutinib may be taken with or without food. Acalabrutinib should be taken under fasting condition (at least 10 hours before dosing and at least 4 hours after dosing) in the Phase 1 portion morning dose of Cycle 0 Day 1 and Cycle 1 Day 8. The capsules should be swallowed intact and subjects should not attempt to open capsules or dissolve them in liquid. Doses should be administrated approximately 12 hours apart, it is recommended that acalabrutinib be taken as close to the scheduled time as possible (preferably within \pm 1 hour). However, if a dose is missed, it can be taken up to 3 hours after the scheduled time with a return to the normal schedule with the following dose. If it has been >3 hours, the dose should not be taken and the subject should take the next dose at the next scheduled time. The missed dose will not be made up and must be returned to the site at the next scheduled visit.

The investigational product, acalabrutinib capsules for oral administration, is supplied as blue and yellow opaque hard gelatinous capsules and is provided in white, high-density polyethylene bottles. Additional information about the investigational product may be found in the Investigator Brochure.

Labels will be prepared in accordance with Good Clinical Practice (GCP) Ordinance. All study drugs should be kept in a secure place under appropriate storage conditions. A description of the appropriate storage conditions is specified in the labels.

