6.5.2 Prohibited concomitant therapy

Any concurrent chemotherapy (e.g., bendamustine, cyclophosphamide, pentostatin, or fludarabine), anticancer immunotherapy (e.g., rituximab, obinutuzumab, alemtuzumab, or ofatumumab), corticosteroids (at dosages equivalent to prednisone >20 mg/day), kinase inhibitors (e.g., ibrutinib, zanubrutinib and idelalisib), bone marrow transplant, experimental therapy, and radiotherapy are prohibited.

Warfarin or equivalent vitamin K antagonists (e.g., phenprocoumon) are prohibited. Any herbal medication is prohibited from Cycle 0 Day 1 to Cycle 1 Day 8 (intensive PK sampling period) in Phase 1 portion. Administration of herbal medication during other treatment period is not recommended, unless it is prescribed by the investigator for treatment of specific clinical events. At study entry, subjects may be using topical or inhaled corticosteroids or

steroids (≤ 20 mg of prednisone or equivalent per day) as therapy for comorbid conditions but use of corticosteroids as therapy of the lymphoid cancer is not permitted.

Immunization with a live virus vaccine is prohibited within 28 days before study treatment and during study treatment.

The effect of agents that reduce gastric acidity (antacids or proton pump inhibitors) on acalabrutinib absorption was evaluated in a healthy volunteer study (ACE-HV-004). Results from this study indicate that subjects should avoid the use of calcium carbonate containing drugs or supplements for a period of at least 2 hours before and at least 2 hours after taking acalabrutinib. Use of omeprazole or esomeprazole or any other proton pump inhibitors while taking acalabrutinib is strongly not recommended due to a potential decrease in study drug exposure. If treatment with an H2-receptor antagonist is required, the H2-receptor antagonist should be taken approximately 2 hours after an acalabrutinib dose.

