8.5 Pharmacokinetics

8.5.1 Collection of pharmacokinetic samples

In Phase 1 portion, venous blood samples for determination of concentrations of acalabrutinib and its metabolite (ACP-5862) in plasma will be taken at the times presented in [Table 11](#) and [Table 12](#). The date and time of collection of each sample will be recorded.

The timing of the pharmacokinetic samples may be adjusted during the study, dependent on emerging data, in order to ensure appropriate characterization of the plasma concentration-time profiles.

Table 11 Pharmacokinetic sampling schedule (Single dose, Phase 1 portion)

Cycle	Day	Pre-dose***	Hours Post-dose										
			0.25 (±1min)	0.5 (±5min)	0.75 (±5min)	1*	2*	4*	6*	8*	12*	24*	48*
0	1	X	X	X	X	X	X	X	X	X	X	X	X**

* Time allowance: ±10 min

** Before Cycle 1 Day 1 morning dose

*** Within 10 min prior to dosing

Table 12 Pharmacokinetic sampling schedule (Multiple doses, Phase 1 portion)

Cycle	Day	Pre-dose***	Hours Post-dose								
			0.25 (±1 min)	0.5 (±5 min)	0.75 (±5 min)	1*	2*	4*	6*	8*	12*
1	8	X	X	X	X	X	X	X	X	X	X**
1	28					X (±0.5 hr)	X (±0.5 hr)	X (±1 hr)			

* Time allowance: ±10 min

** Before Cycle 1 Day 8 evening dose

*** Within 10 min prior to dosing

In Phase 2 portion, the schedule of sparse PK sampling for determination of acalabrutinib plasma concentration is presented in [Table 13](#).

Table 13 Sparse pharmacokinetic sampling schedule in Phase 2 portion

Cycle	Day	Hours Post-dose		
		1 (\pm 0.5 hr)	2 (\pm 0.5 hr)	4 (\pm 1 hr)
1	8	X	X	X
1	15 or 22	X	X	X

All timepoints are relative to the morning dose.

Samples will be collected, labelled, stored and shipped as detailed in the Laboratory Manual.

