4.2.6. Pharmacokinetic analyses

All PK analyses will be summarized based on the PK analysis set. The data excluded from the PK analysis set will be flagged in subject listing only.

Precision and rounding rules for pharmacokinetic data

For PK concentration data, the listings will be presented to the same number of significant figures as the data received from the bioanalytical laboratory; for PK parameters, the listings will be presented according to the following rules:

- Cmax, Cmin – will be presented to the same number of significant figures as received from the bioanalytical laboratory.
- tmax, λz lower and upper time limit – will be presented as received in the data, usually to 2 decimal places
- AUCinf, AUClast, AUC0-12, AUC τ , $t_{1/2}\lambda z$, CL/F, Vz/F, Rac ratios, metabolite to parent ratios, Rsq, Rsq adj, λz span ratios – will be presented to 3 significant figures
- λz – will be presented to 4 significant figures
- λz , N – will be presented as an integer (no decimals)
- Tlast - will be presented as received in the data, usually to 2 decimal places

- AUCextr – will be presented to 3 significant figures

For PK concentration data all descriptive statistics will be presented to 4 significant figures with the exception of the minimum and maximum which will be presented to 3 significant figures.

For PK parameter data the descriptive statistics will be presented according to the following rules:

- Cmax, Cmin, AUCinf, AUClast, AUC0-12, AUC τ , $t^{1/2}\lambda_z$, CL/F, Vz/F, Rac ratios and metabolite to parent ratios descriptive statistics will be presented to 4 significant figures with the exception of the minimum and maximum which will be presented to 3 significant figures
- tmax – all descriptive statistics will be presented as received in the data, usually to 2 decimal places
- λ_z – all descriptive statistics will be presented to 5 significant figures with the exception of the minimum and maximum which will be presented to 3 significant figures

Source data shall be used in all derived PK parameter calculations without prior rounding.

Phase 1 portion

Plasma concentrations of acalabrutinib and a metabolite (ACP-5862) will be summarized by nominal sample time. Plasma concentrations at each time point will be summarized by the following summary statistics:

- The geometric mean (gmean, calculated as $\exp[\mu]$, where μ is the mean of the data on a logarithmic scale)

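### The Cycle 1 Day 28 PK samples are meant to show time-dependent change, but the SAP gives them only nominal-time group summaries despite windows of up to ±1 h; add a within-subject comparison at actual times

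*Protocol*

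**What the plan says.** **Purpose.** Protocol 4.1, repeated in the synopsis and in SAP 1.2, gives the Day 28 samples one role: "Additional sparse PK samples will be collected on Cycle 1 Day 28 to assess time-dependent changes".

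**Windows.** Protocol 8.5.1, Table 12, schedules 1, 2 and 4 h samples on both Cycle 1 Day 8 and Cycle 1 Day 28. On Day 8 these carry the note "Time allowance: ±10 min". On Day 28 the table entries are ±0.5 h, ±0.5 h and ±1 h.

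**Dosing conditions.** Fasting is required "in the Phase 1 portion morning dose of Cycle 0 Day 1 and Cycle 1 Day 8"; otherwise "Acalabrutinib may be taken with or without food" (Protocol 6.1.1). Protocol 6.5.2 states: "Any herbal medication is prohibited from Cycle 0 Day 1 to Cycle 1 Day 8 (intensive PK sampling period) in Phase 1 portion". It continues: "Administration of herbal medication during other treatment period is not recommended, unless it is prescribed by the investigator". Exclusion criterion 24 also bars subjects with "expected requirement for use of a CYP3A inhibitor or inducer (including herbal medication known to modulate CYP3A4 enzyme activity) during the first 28 days" of study drug administration.

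**Analysis.** SAP 4.2.6 states: "Plasma concentrations of acalabrutinib and a metabolite (ACP-5862) will be summarized by nominal sample time". Mean plots also use nominal time. Samples outside their window are left out of summary tables and mean plots. Individual plots use actual times, and the listings show actual elapsed time and its difference from nominal. Non-compartmental parameters use actual times (Protocol 9.4.1.2) but are derived only for Cycle 0 Day 1 and Cycle 1 Day 8 (also SAP 3.2.3). Neither document defines a comparison of Day 28 with Day 8.

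**The concern.** The samples have a stated purpose but no analysis suited to it. In the group outputs, a Day 28 sample drawn at 3 h or 5 h is inside its window and counts as a 4 h value. Beside the Day 8 summary at 4 h, where every sample lies within 10 minutes of nominal, the difference mixes any real change with the effect of sampling time. For a drug with a half-life near 1 h that effect is large.

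PK is a primary objective of Phase 1, which plans about 12 subjects and at least 8 evaluable profiles (Protocol 9.2). With so few, a timing difference could be read as a change in exposure after Day 8, or could hide one. Fasting status and the herbal rule also differ between the two days, so the dosing conditions are not matched either.

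**Working it through.** The documents give no precision or power figure for the Day 28 data, so there is no figure to reproduce. The check asks how far a concentration can move from sampling time alone when nothing else changes.

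**Inputs**
- Half-life about 1 h at 100 mg BID; means from 0.97 to 2.1 h in healthy subjects (Protocol 2.2.3.3).
- tmax 0.5 to 1.0 h (same section).
- Windows w from Table 12: 1/6 h on Day 8; 0.5 h (1 and 2 h samples) and 1 h (4 h sample) on Day 28. Ratios: 0.5/(1/6) = 3 and 1/(1/6) = 6.
- n = 12 or 8.
- Assumption: actual times are uniform within the window. No biological between-day variability is added.

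**Single sample, elimination phase.** With k = ln 2 / half-life, a sample at the edge of its window differs from the nominal-time value by a factor exp(±k·w).

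| Sample | Half-life 1 h | Half-life 2.1 h |
|---|---|---|
| Day 8, ±10 min | 0.89 to 1.12 | 0.95 to 1.06 |
| Day 28, 2 h, ±0.5 h | 0.71 to 1.41 | 0.85 to 1.18 |
| Day 28, 4 h, ±1 h | 0.50 to 2.00 | 0.72 to 1.39 |

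**Spread on the log scale.** Uniform timing gives SD = k·w/√3. At half-life 1 h this is 0.693/√3 = 0.40 for Day 28 at 4 h and 0.693/(6√3) = 0.067 for Day 8. At 2.1 h the Day 28 value at 4 h is 0.330/√3 = 0.19.

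**Group ratio at 4 h, half-life 1 h, n = 12.** The SD of a within-subject log ratio is √(0.40² + 0.067²) = 0.406. The timing-only 95% range of the geometric mean ratio is exp(±1.96 × 0.406/√12) = 0.80 to 1.26. If both days had ±10 min, it would be exp(±1.96 × 0.067 × √2/√12) = 0.95 to 1.05.

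Simulation of a one-compartment oral model with no true change agrees:
- 4 h, half-life 1 h, n = 8, tmax 0.5 h: 0.76 to 1.32.
- 4 h, half-life 2.1 h, n = 12: 0.90 to 1.11.
- 2 h, half-life 1 h, n = 12: 0.89 to 1.13 (tmax 0.5 h) or 0.92 to 1.07 (tmax 1.0 h).

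**Bias.** Symmetric random timing leaves the geometric mean ratio at about 1 in the elimination phase. It raises the arithmetic mean at 4 h by sinh(0.693)/0.693 = 1.08, about 8%, at half-life 1 h. At the 1 h time point with tmax 1.0 h, the Day 28 window straddles the peak and the geometric mean ratio is about 3 to 4% low. Larger bias needs systematic timing: if every 4 h sample were 30 minutes late, the ratio would be 2^(−0.5) = 0.71, an apparent fall of 29%. Nothing in the documents says this will happen.

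**Not sized.** The documents give no food-effect figure, no general figure for herbal medication and no half-life for ACP-5862. The results above concern timing and the parent drug only.

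**The case against.** The strongest reply is that nothing formal depends on the Day 28 data. The time-dependence parameter is TCP, the Day 8 AUC over the dosing interval divided by the Cycle 0 Day 1 AUC to infinity. It and the accumulation ratios use two fasted days with tight windows and actual times. A reader might infer that the primary PK objective, or the trial's check on time dependence as a whole, is compromised. The documents do not support that. They also plan no nominal-time test of Day 28 against Day 8 that could be called wrong.

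The artefact is also visible, because actual times appear in the listings and individual plots. The Day 28 windows match the Phase 2 sparse schedule in Table 13 and look like an ordinary sparse-sampling allowance. The factors of 0.5 and 2.0 are extremes for one sample at the edge of the widest window.

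A reader might also infer that food or herbal use will produce an apparent change. The differences in conditions are real, but their effect cannot be sized. The herbal difference is softened by the advice against use after Day 8, the caution in Protocol 5.3, the advice to avoid strong CYP3A modulators and exclusion criterion 24. That criterion is applied at entry and covers 28 days of dosing, whereas nominal Cycle 1 Day 28 is study day 30 counted from Cycle 0 Day 1.

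All of this stands and limits the point. It does not remove it: TCP cannot show a change after Day 8, only the Day 28 samples can within Phase 1, and seeing actual times in a listing is not an analysis.

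**Conclusion.** The point holds as a modest improvement to the plan. The nominal-time summaries serve the samples' only stated purpose poorly, because at 4 h random timing alone could move the group ratio by roughly 20 to 26% either way with 12 subjects and a half-life of 1 h, or by about 10% at 2.1 h. This rests on uniform in-window timing, a one-compartment shape, and the protocol's half-life and tmax for the parent drug. Random timing mainly adds noise to the geometric mean; bias of consequence needs systematically early or late sampling, with a small bias also possible near tmax. The differences in food and herbal conditions are a reason for caution in interpretation, not evidence of an effect of known size.

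**What to change.** In SAP 4.2.6, add the following for Cycle 1 Day 28, leaving the existing outputs in place:

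1. For each subject and analyte, divide each Day 28 concentration by that subject's Day 8 concentration interpolated at the same actual elapsed time, using the linear-up/log-down rule already in SAP 3.2.3. The Day 8 samples from 0.25 to 12 h bracket every permitted Day 28 time.
2. Summarize the ratios as a geometric mean ratio with its range or a descriptive confidence interval. Give main weight to 2 h and 4 h; treat 1 h as supportive, because its 0.5 to 1.5 h window spans the stated tmax range.
3. Flag samples with recorded herbal or CYP3A-active co-medication, and fed state where known.
4. State that the nominal-time Day 28 summaries are descriptive and do not by themselves support a conclusion on time dependence.

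No dosing or co-medication rule needs to change. Collection times, diary dose times and concomitant medications are already recorded. The cost is SAP wording and a small derivation, with some interpolation error near tmax and least at 4 h, where the timing problem is largest.
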